Mechanisms of Pain. Acute pain is a centrally mediated sensation driven primarily by nociceptive input conducted by A δ and C fibers responding to noxious stimulation or tissue injury in the periphery. An individual's experience of pain is modulated by the activity of a well-characterized set of neural structures involved in the contextualization and evaluation of the nociceptive stimulus, including those involved in sensory processing (primary and secondary somatosensory cortices), executive control (prefrontal and anterior cingulate cortices, anterior insula), and limbic processing (amygdala, hippocampus) (Apkarian et al., 2005; Clarke and Lawrence, 2013; Craggs et al., 2007; Staud et al., 2008). In 80-90% of cases, acute pain resolves as peripheral damage is repaired. In some cases, however, patients' pain persists even after no peripheral damage remains. In order to capitalize on the high degree of controllability and repeatability afforded by laboratory pain induction techniques, we propose the use of experimental heat pain stimulation for this project. This is a common technique used to assess pain psychophysics and neural mechanisms of pain which our research group has successfully employed many times (e.g., Craggs et al., 2012; Letzen et al., 2015; Sevel et al., 2015a; Sevel et al., 2015b).

Relief of Pain as Reward. Because pain is, by definition, an aversive sensation (International Association for the Study of Pain, 1979), the cessation of pain is associated with relief. Although conceptually distinct from typical appetitive rewards like

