General Approach. For this study of healthy, community-dwelling moderating drinkers, we propose a repeated-measures, double-blind placebo-controlled factorial design with FH of alcoholism (+/-) and sex as between-subjects factors and alcohol administration (Alcohol Dose: placebo, 0.08 g/dL) as a within-subject factor. The study will include equal numbers of men and women. Study procedures will occur in the Center for Pain Research and Behavioral Health of the University of Florida under supervision of the PI (JB). The investigative team, including the PI; Drs. [name], [name], and [name]; and research assistants, will meet on a bi-weekly basis over the course of the project to

ensure successful completion. Recent progress regarding all aspects of the study will be addressed during these meetings, including ongoing review of recruitment practices and behavioral and imaging data quality. Drs. [name], [name], [name], and [name] will also work together to ensure all research assistants are fully trained to conduct the project.

Methods

Participants. Healthy volunteers (N=220; 110 women) will be recruited for the study via flyers, word of mouth, and internet and local radio advertisements with the aim of obtaining 110 completers; 55 women). Individuals aged 21-45 years will be recruited in order to avoid confounding effects of binge-drinking patterns associated with college-aged individuals and the apparent increased susceptibility of older adults to the acute neurobehavioral effects of alcohol (e.g., [name] et al., 2014). We plan to enroll a representative sample of participants from our recruitment area in north central Florida (i.e., 65% white, 23% black, 7% Asian, 5% other), including ~10% identifying as Hispanic or Latino (see targeted recruitment table).

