Laboratory Sessions. Consistent with previous work ([name], et al., 2014; Lewis, et al., 2013), participants will be asked to fast for at least 4 hours prior to their scheduled session and abstain from consuming any alcohol in the 24 hours before laboratory sessions. Taking normal morning medications will be permitted, but no other OTC or prescribed medications (including allergy medications and analgesics) will be allowed on the day of testing. **Following provision of a urine sample, a drug screening will be performed. This screen will test for tetrahydrocannabinol, cocaine, benzodiazepines, morphine, and methamphetamine (Innovacon, Inc., San Diego, CA).** Participants testing positive for any of these drugs will be discontinued. **A baseline breath alcohol concentration (BrAC) measure will be taken, which must be 0 g/dL.** Women will complete a brief questionnaire regarding their menstrual cycle, including: 1) if they are currently menstruating or if they are post-menopausal; 2) the length of their menstrual cycle; 3) how many days have elapsed since their last menses began; 4) how long their menses typically lasts; and 5) if they use any hormonal preparations (e.g., birth control). **Women of child bearing potential will also be given a pregnancy test; should a woman's pregnancy test be positive, she will be excluded from the study with a recommendation to contact her physician. Women who are currently breastfeeding will also be excluded.** All testing will be conducted in private rooms within the Center for Pain Research and Behavioral Health. Participants will be provided with a light breakfast one hour before alcohol administration (~200 kcal). Following breakfast, participants will repeat affective measures (BDI-II/STAI) as well as an Irritability Questionnaire (IRQ; Craig et al., 2008). Lunch will be provided following testing, as well as another light meal should a participant be retained in the Center during dinner hours while their BrAC levels drop. For laboratory sessions, the PI or a research assistant will schedule a ride with Uber or Lyft to drive participants home after the completion of the session. Research assistants will use the GPS features of the rideshare app to ensure that participants make it home safely. If the rideshare app indicates that the participant was dropped off somewhere other than the vicinity of their home, the attending researcher will call the number left by the participant and speak with the participant. If the participant does not answer the phone, the researcher will contact the IRB to report the protocol deviation. Participants will be paid \$120 for completing each laboratory session (or \$15/hour up to \$120 for non-completers). Laboratory sessions will be separated by at least 48 hours.

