
Alcohol Administration. Alcohol administration procedures are consistent with those used by Drs. [name] and [name] in their previous work, as well as NIAAA guidelines for the safe and ethical administration of alcohol in experimental settings (Brown et al., 2014). Participants will complete two laboratory sessions in which they will be administered one of two beverages: placebo (0.00 g/dL target BrAC) or active alcohol (0.08 g/dL target BrAC). Session order will be counterbalanced across participants. For laboratory sessions in which a participant will be given the active dose, the quantity of medical grade alcohol (100% or 95% ethanol) needed to achieve 0.08 g/dL will be calculated using a modification of the Widmark formula. The medical (United States Pharmacopeia) grade ethanol used in this study will be obtained from standard laboratory supply providers (e.g., Fisher Scientific). The Widmark formula

utilizes age and weight measures for men and height and weight measures for women (Watson, et al., 1981; Widmark, 1932). Only research assistants over the age of 21 will be involved in drink mixing/administration procedures, and all research assistants will be trained by the PI in drink mixing/administration procedures. In order to maintain the study's double blind, a researcher not involved in QST will be responsible for calculating alcohol doses and mixing drinks, and the dose calculation and mixing procedure confirmed by a second research assistant. Alcohol will be mixed with ice-cold sugar-free lemon-lime soda in a 1:3 ratio and split into two servings ([name], et al., 2014; Gilbertson, et al., 2009; Harrison et al., 2007). Placebo beverages will consist of only vehicle. Participants will consume both servings within 5 minutes, and both active and placebo drinks will be misted with alcohol to enhance placebo effectiveness. A small amount of alcohol will be placed on the rim of the glass and the surface of the drink in order to further mask the study condition. Participants will rinse their mouths thoroughly with water once their beverage has been consumed. To avoid influencing participants' expectations regarding alcohol analgesia, no suggestion regarding the potential pain-relieving effects of alcohol will be provided before or after beverage administration.

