BrAC/BAC Assessment. Blood alcohol concentration (BAC) will be estimated using two methods. Following beverage administration, breath alcohol concentration (BrAC) measures will be obtained every 10 minutes using standard a handheld breath analysis device (e.g., Intoxylizer 400PA, CMI, Inc., Owensboro, KY) until the participant is placed in the MRI device (i.e., 2 measurements). After this point, BAC will be approximated using salivary alcohol testing strips (QED Saliva Alcohol Test, OraSure Technologies, Inc. Bethlehem, PA), with collection occurring after each scan is completed (resulting in 3 measurements occurring over the duration of scanning). Following scanning, breath measures will again be taken periodically until the participant's BrAC is ≤ 0.02 , consistent with NIAAA guidelines (Brown et al., 2014). They will then be transported home.

Subjective Intoxication and Placebo Effectiveness. Participants will complete 10cm VAS measures of subjective intoxication (anchored from 'not at all intoxicated' to 'most intoxicated imaginable') (Harrison, et al., 2007). These assessments will be administered concurrently with each BrAC assessment, as well as immediately before and after QST assessments and functional image acquisitions. In order to assess the contribution of subjective stimulatory and depressant effects of alcohol to alcohol analgesia, the Subjective Effects of Alcohol Scale (SEAS; Morean et al., 2013) will also be administered immediately prior to QST assessments and the fMRI heat pain paradigm, providing measures of positive and negative aspects of stimulation and sedation (i.e., HIGH+/- and LOW+/-). At the conclusion of testing, participants will be asked whether they believe they received an alcoholic beverage; those who indicate they did not receive a beverage will be asked when they made that determination.

QST Procedure. QST testing will occur in a private room within the Center for Pain Research and Behavioral Health during screening procedures and within the scanner suite during laboratory sessions. First, during screening, all subjects will undergo a set of calibration trials to establish individualized temperatures to be used during laboratory

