sessions so that degree of analgesia achieved from beverage consumption can be assessed relative to a personalized baseline. These calibration trials will consist of an ascending series of thermal pulses starting at 43°C and increasing by 1°C until the participant's tolerance is reached. After each pulse, participants will rate pain intensity using a visual analog scale (VAS). The lowest temperature with a VAS score of 5 will be used for thermal stimuli during laboratory sessions. Next, during both screening and laboratory sessions, we will employ a slowly ramping thermal stimulus (.5°C per second starting at 32°C) delivered to the glabrous skin of the foot. Pain ratings (using a 10 cm VAS ranging from "no pain" to "most intense pain imaginable") will be collected every 5 seconds during this process until the participant's tolerance is reached in order to determine temperatures associated with pain threshold (i.e., temperature at which the stimulus first becomes painful) and tolerance (i.e., temperature at which the stimulus becomes unbearable). This protocol also allows for the examination of pain after-sensation following removal of the thermal probe, a construct related to the clinical experience of chronic pain (Staud et al., 2007). To this end, participants will report current pain levels at 15 and 30 seconds following stimulus removal. VASs are considered the "gold standard" for laboratory and clinical pain assessment given that they have a ratio scale (Price et al., 1983) and are able to effectively separate the sensory (i.e., intensity) and affective (i.e., unpleasantness) components of the pain experience. The investigative team has extensive experience with these procedures, and is confident they can be completed safely and effectively. All thermal stimuli will be delivered using a computer-controlled Q-Sense fMRI Compatible thermal stimulator (Ramat Yishai, Israel), a Peltier-element based device. We propose to utilize a thermal stimulus paradigm because the processing of such stimuli is particularly well understood. Such paradigms have been demonstrated in the broader pain literature to be sensitive to group differences (e.g., chronic pain patients vs. healthy controls), as well as experimental manipulations like acute opioid analgesic treatment and placebo induction (e.g., Chung et al., 2007; Sevel et al., 2015; Staud et al., 2012). Furthermore, its use in this study will enhance comparability to previous work. Following each QST measure during laboratory sessions, participants will be provided with a 10 cm VAS assessing perceived relief from pain resulting from beverage consumption (anchored from "No relief at all" to "Most profound relief imaginable"). QST procedures will require approximately 10 minutes. During laboratory sessions, QST procedures will be administered prior to alcohol consumption to function as a point of reference for participants and again approximately 15 minutes after beverage consumption to allow for absorption of alcohol ([name] et al., 2014).

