with no adverse consequences; 3) the level of pain experienced by participants is below their tolerance level; and 4) although pain sensation may continue after thermode removal (at discretion of the participant), this is not expected to last longer than 90 seconds. Furthermore, because QST instrumentation cannot produce thermal stimuli above 52°C and is equipped with an automatic shutdown system (preventing prolonged delivery of high-intensity stimuli) the risk of burning the skin is very slight. Of over 800 participants tested with QST procedures in the Center for Pain Research and Behavioral Health over several studies, less than 1.5% have suffered a first-degree burn, less than 0.5% have suffered a second-degree burn, and none have suffered a third-degree burn. Should a participant suffer a burn following thermal QST or continued pain 24 hours after pressure pain QST, an adverse event will be reported to the IRB.

Participant Confidentiality Risks. The investigative team places a high priority on protection of patient confidentiality and will use the following procedures to protect patients. Unique participant identifiers will be generated in order to collect protected health information (i.e., from questionnaires) for research purposes. Paper questionnaires and forms will be stored in a locked storage space, digital information will be stored in encrypted, password protected files on secure servers, and the data that links the participants to their unique identifiers will be stored in a separate location. When the study is completed and all raw data is entered electronically, participant identifiers will be destroyed. Despite these efforts, it is possible that participant confidentiality may be breached. If a breach occurs, it will be reported to NIH and the IRB and appropriate measures will be taken. These measures include but are not limited to informing affected participants of the breach and assisting with protective measures once the breach is detected.

Data and Safety Monitoring Plan

Because the proposed study does not comprise a clinical trial, a formal Data and Safety Monitoring Board has not been planned. The investigative team, including Drs. [name], [name], [name], and [name], will meet quarterly to discuss data and safety monitoring issues. Any issues identified during the course of these meetings will be handled in a manner consistent with the University of Florida's policies.

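### The only reporting rule for persistent pain is tied to pressure testing, which this heat-only study does not describe, so burn-free pain 24 hours after heat has no stated criterion

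*Combined protocol and SAP*

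**What the plan says.** Section 7, under QST Discomfort and Risks, closes with two events that lead to an IRB report after pain testing: "a burn following thermal QST or continued pain 24 hours after pressure pain QST, an adverse event will be reported to the IRB". The first is a burn after thermal testing. The second is pain still present a day after pressure testing.

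The stimulus is settled in section 4, under Mechanisms of Pain, where the protocol states: "we propose the use of experimental heat pain stimulation for this project". The Research Plan follows this. QST Procedure describes heat pulses for calibration and a heat ramp for threshold and tolerance. fMRI Heat Pain Protocol describes blocks of heat to the sole of the foot.

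Two other statements concern pain after the probe is removed. QST Procedure says that "participants will report current pain levels at 15 and 30 seconds following stimulus removal". The risk paragraph adds that any such pain is expected to be over within 90 seconds.

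**The concern.** A reporting rule works only if the event it names can occur in the study. This one makes pain at 24 hours reportable after a type of stimulus that the protocol does not describe, and is silent about the type it does use. The authors evidently judged pain lasting a day to be worth an IRB report. That judgement should apply at least as much to heat, which participants receive at screening and in both laboratory sessions.

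At stake is the consistency of safety reporting. Suppose a participant mentions a sore foot the day after a session and no burn is visible. The written rule gives staff nothing to apply, although by the protocol's own expectation the pain should have gone within 90 seconds. The visible text leaves the decision to general arrangements that set no threshold for pain.

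**Working it through.** No arithmetic applies. The check compares the stimuli described with the reporting criteria stated, then looks for any other text that could fill the gap.

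**Step 1. Stimuli described for this study**

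- Modality chosen (section 4, Mechanisms of Pain): heat.
- Calibration at screening (section 6, QST Procedure): rising heat pulses from 43°C.
- Threshold and tolerance at screening and in laboratory sessions (same place): a heat ramp from 32°C.
- Scanner task (section 6, fMRI Heat Pain Protocol): heat blocks at the individually calibrated temperature.
- The risk paragraph in section 7 itself opens by describing QST as causing thermal pain.

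Pressure procedures described: none. Apart from the reporting sentence, pressure pain appears only in the Background account of earlier studies and in the title of one reference.

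**Step 2. Reporting criteria stated for pain testing**

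| Event | After heat | After pressure |
|---|---|---|
| Burn | Reportable, no time limit | Not mentioned |
| Pain at 24 hours without a burn | No criterion | Reportable |

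The one persistent-pain criterion sits in the column for which the study has no procedure. The cell that applies to this study is empty.

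**Step 3. Whether other text fills the empty cell**

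- The 90-second figure is an expectation about duration. It does not say what happens when the expectation fails.
- The ratings at 15 and 30 seconds are a research measure of after-sensation, and they stop long before 24 hours.
- The Data and Safety Monitoring Plan has the team meet quarterly and handle identified issues under University policy. It sets no criterion for pain.
- The bi-weekly team meetings in General Approach review study progress and data quality. They set no criterion for pain either.

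None of these supplies the missing criterion.

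**Step 4. Whether the fMRI heat runs are covered**

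The sentence names thermal QST only. Elsewhere the protocol treats the two as distinct: the subjective-effects scale is given "immediately prior to QST assessments and the fMRI heat pain paradigm". Read strictly, the scanner runs are not named. In practice this matters little. In each laboratory session "QST procedures will be administered prior to alcohol consumption" and again about 15 minutes after the drink, so a burn found after scanning would also follow thermal QST. This is a point of wording to tidy in the same edit.

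**The case against.** The strongest reply is that this is a slip of one word with a narrow consequence. Any burn after thermal QST is reportable, with no time limit and no minimum severity, and the paragraph counts first-degree burns in its own safety record. The device cannot exceed 52°C and shuts down automatically. What remains is pain at 24 hours with no burn of any degree, which may never occur. Listing events that will be reported does not say that others will not be, and the team meetings and University policy are further routes. The removed consent pages may also tell participants to report lasting pain.

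Most of this stands, and it is why the point is minor. It does not rescue the sentence: none of those routes states a criterion for pain after heat, and the criterion that is stated cannot be met.

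A reader might infer more, and the documents do not support it:

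- *That heat injuries would go unreported.* Burns are covered, and the protocol does not exclude reporting other events.
- *That the many heat applications per participant measure the size of the problem.* Counting exposures, or comparing 24 hours with 90 seconds, measures neither harm nor missed reports. The documents give no rate for this event.
- *That the absence of a written foot inspection is itself a defect.* A protocol need not write out each bedside check. Staff place the probe on the foot, and participants may stop any procedure. An inspection and rescheduling rule would be a separate preference and does not follow from the misworded trigger.

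**Conclusion.** The reporting sentence is wrong as written, and the weight is minor. Its persistent-pain criterion cannot be triggered by any procedure the protocol describes, and burn-free pain lasting 24 hours after heat has no stated reporting criterion. The number of participants affected is unknown and may be zero. Efficacy analyses, sample size and power do not change.

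The conclusion rests on reading the study as heat-only, which every description of a stimulus supports. If a pressure procedure is intended, the 24-hour rule would apply to it, but the procedure would then be missing from the Research Plan and heat would still lack a criterion. The conclusion concerns what the visible protocol states. It makes no claim about how staff would act in a particular case, or about what the removed consent pages say.

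**What to change.** In section 7, QST Discomfort and Risks, reword the trigger so that the IRB receives an adverse event report for *a burn, or pain at the test site continuing 24 hours, following thermal QST or the fMRI heat pain runs*. This corrects the stimulus and names the scanner runs in the same edit. If pressure testing is planned, describe it under QST Procedure and keep its 24-hour trigger alongside the heat one.

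The cost is one phrase. The possible downside is a slightly higher count of reported events.

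No new inspection or rescheduling rule is needed. At most, staff could ask at the second laboratory session whether pain persisted after the first. The protocol says "Laboratory sessions will be separated by at least 48 hours", so the answer can establish whether pain lasted 24 hours. That question would cover only the first laboratory session. No interval is stated between screening and the first laboratory session, and no visit follows the second. It is optional, and the rewording does not depend on it.
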